- For subjects on the episodic regimen following the end of a surgical/rehabilitation period, the efficacy period for the episodic regimen starts or re-starts (depending on whether there is a treatment regimen change during the surgical/rehabilitation period) at 00:01 on the day following the end of the surgical/ rehabilitation period.

Start and end dates/times for the efficacy period for given treatment regimens and treatment regimen changes will be adjusted for each surgery (major or minor) as necessary.

For subjects on a prophylactic regimen before the start of a surgical/rehabilitation period, the interval of time between the last dose before a surgical/rehabilitation period and the start of the surgical/rehabilitation period will not be attributed to the efficacy period for the prophylactic regimen. By definition, there should not be any treated bleeding episodes in this interval of time.

For subjects on a prophylactic regimen following the end of a surgical/rehabilitation period, bleeding episodes that occur after discharge from a rehabilitation facility but before the next prophylactic dose will be attributed to the surgical/rehabilitation period and hence not counted towards the annualized bleeding rate.

Adjustments Due to Large Injection Intervals

For analysis purposes, the efficacy period will also be adjusted to account for large intervals between injections resulting from missing data. Time between any 2 adjacent rFVIIIFc injections of greater than 28 days within a prophylactic treatment regimen will be removed from the efficacy period. The efficacy period prior to each such interval will end at the time of the first

injection of this interval and restart (or start if it is the first interval of a treatment regimen) at the time of the second injection of this interval. The efficacy period will be adjusted for each identified interval that is not within a surgical/rehabilitation period. Treatment regimens considered for large interval adjustment include tailored prophylaxis, weekly prophylaxis and personalized prophylaxis regimen with at least 2 routine prophylactic injections (additional injections are not considered due to the sporadic nature of these injections). No adjustment for large injection intervals will be made for episodic treatment regimens.

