7.1.1. Bleeding Episodes

Bleeding episodes will be recorded in both the EPD and eCRF; this information will be used to derive the secondary efficacy endpoints. During the course of the study the investigator was given the opportunity to disagree with the type of bleed (spontaneous, traumatic) as classified by the subject/caregiver and the subject/caregiver was subsequently given the opportunity to agree or disagree with the reclassification. If the subject/caregiver agreed with the Investigator's assessment, then all analyses subset by type of bleed will be based on the Investigator's determination of the bleed type whether or not the change was made to the subject's records.

A standardized definition of a bleeding episode has been applied to this study, as follows. A bleeding episode starts from the first sign of a bleed, and ends no more than 72 hours after the last treatment for the bleed, within which any symptoms of bleeding at the same location, or injections less than or equal to 72 hours apart, are considered the same bleed. Any injection to treat the bleed taken more than 72 hours after the preceding one will be considered the first injection to treat a new bleed. For the purpose of analysis, the latter injection will be associated with a new bleeding episode and classified as type=Unknown. The location(s) associated with the original bleeding episode will be carried forth to the new bleeding episode; the onset date and time of bleeding will be unknown and hence considered missing. Any bleeding at a different location is considered a separate bleeding episode regardless of the time from the last injection.

This algorithm will also apply when a follow-up injection was recorded subsequent to a prophylactic injection. If the follow-up injection was administered >72 hours after the previous injection to treat a bleeding episode (type=spontaneous, traumatic, follow-up), then the follow-up injection will be classified as a new bleeding episode as described above.

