Bleeding at a different location will occur when the general bleeding location is different (e.g., in a joint for the original bleeding episode and subsequently in a muscle) or in a sub-location not initially present if in the same location category (e.g., right elbow for the original bleeding episode and subsequently in the right and left elbows). Conversely, a bleeding episode that originally occurs in the right elbow and left knee and is reported as a new bleed within 72 hours as being only in the right elbow will be considered to be in the same location and hence not counted as a new bleeding episode.

A bleeding episode that occurs in multiple locations will be counted as a single event when determining the overall annualized number of bleeding episodes. However, in summaries by bleeding location, the bleeding episode will be counted in each location for which it is reported with the exception that bleeding that occurs in more than one sub-location of the same location category (e.g., 2 or more different joints) will be counted as just one for that location category.

Only bleeding episodes that were treated with at least one dose of FVIII (whether rFVIII-Fc or a non-study drug) will be included in the analysis of endpoints evaluating bleeding. That is, bleeding episodes that were not treated at all will not be included. Bleeding episodes that were treated with non-study medication will be included in the determination of the annualized bleeding rate. The handling of bleeding episodes treated with non-study FVIII for other endpoints is discussed in Sections 7.4.1.

Bleeding episodes of an unknown type will be included in the determination of the annualized bleeding rate and in summaries based on bleeding episodes but, unless specified otherwise, will not be included in summary tables where endpoints are summarized by type of bleed.

The per-subject annualized number of bleeding episodes, hereafter referred to as the annualized bleeding rate (ABR), will be calculated for each subject using the following formula:

$$\text{ABR} = \frac{\text{Number of bleeding episodes during the efficacy period}}{\text{Total number of days during the efficacy period}} \times 365.25$$

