Inj Reason	Reason of injection changed (other than routine prophylaxis or other to surgical prophylaxis if a confirmed minor/major surgery or procedure is capture in the eCRF during the defined surgical period or date of procedure; or from new bleed to follow up)	Y
Inj Reason Surgery	Injection reason from routine prophylaxis or other to surgical prophylaxis	N
BLD LOC	Change in Bleed Location	Y
BLD TYP	Change in Bleed Type	Y
BLD SYM	Change in Bleed Symptoms	Y
DTOB	Date and/or time of bleed corrected	Y
Activity	Change in Physical Activity question	Y
TRT SD	Amendment to Treat with Study Drug item: “Did you inject with rFVIIIFc (Study Drug)?”	Y
TRT BLD	Amendment to Treat Bleed item: “How did the bleed respond to injection on ...”	Y
Abandon	Query request was raised but then cancelled by site	N
In-clinic administration	In-clinic administration entered in EPD and corrected in reference to source records	N
NBTFU	Injection to treat the bleed is < 72 h of the previous injection to treat the existing bleed New bleed deleted, follow up inj to existing bleed added (per protocol definition)	N
Tx Arm/Reg	Change in treatment arm or regimen	N
ADMIN	Changes made by site to data fields that the site would have entered originally and/or are administrative. E.g. study name or data entered into an incorrect field and corrected, data entered that is not required, expiry date of IMP extended, data field changes that are duplicated due to multiple site staff involved in the query process or similar, correction of injection reason related to treatment arm, e.g. routine prophylaxis to weekly dose for subjects on a weekly regimen	N

In certain circumstances, where subjects could not enter records directly into the EPD for any reason, records were requested to be created manually by the site according to a pre-defined documented process which included SDV by CRA. However, it was subsequently identified that confirmation of SDV could not be provided. Records were re-SDVed at site to determine whether source was available, or whether contemporaneous documentation of confirmation with the subject was available. *(Not discussed further in this SAP).*

For the impact assessment, all data record changes requiring subject confirmation will be set back to the original values. Although changes classified as SVC/L60 did not require subject confirmation (as agreed with MHRA in 2014), these changes will no longer be made directly into

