the data, but will be applied via a programmatic data convention (described in Section 5.4). Manually created data without complete SDV of the record versus a paper diary will be considered unsupported by SDV at site, and will be removed for the purpose of the impact assessment. SDTM and ADAM datasets will be re-created and certain statistical analyses re-run. Endpoints covered under the impact assessment include:

- exposure
- annualized number of bleeding episodes per subject (ABR)
- subjects assessment of response to treatment with rFVIII Fc for bleeding episodes
- number of injections and dose per injection of rFVIII Fc required to resolve a bleeding episode
- prophylactic dose and dosing interval

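### In the SAP Section 9 impact assessment, removing unsupported manual records takes out bleeds and doses but keeps their time on the episodic regimen and in prophylaxis gaps of 28 days or less

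*SAP*

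**What the plan says.** SAP Section 9 describes an impact assessment made under a commitment to a regulator. It has two data steps. First, "all data record changes requiring subject confirmation will be set back to the original values". Second, for records that sites created because a subject could not use the diary: "Manually created data without complete SDV of the record versus a paper diary will be considered unsupported by SDV at site, and will be removed". Then "SDTM and ADAM datasets will be re-created and certain statistical analyses re-run". The endpoints re-run include ABR, exposure, prophylactic dose and dosing interval. Section 9 gives no rule for the time that the removed records covered.

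The general rules therefore decide:

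- **ABR (SAP 7.1.1)** is "Number of bleeding episodes during the efficacy period" divided by "Total number of days during the efficacy period", times 365.25.
- **Prophylaxis time (SAP 5.3.2)** loses any gap between adjacent injections of more than 28 days. The SAP presents this as an adjustment for missing data. Shorter gaps stay in.
- **Episodic time (SAP 5.3.2):** "No adjustment for large injection intervals will be made for episodic treatment regimens".
- **End of the last regimen (SAP 5.3.1)** is the last dose on prophylaxis, but the last study visit (other than safety follow-up) on the episodic regimen.
- **Weekly dose and dosing interval (SAP 6.5.3)** are built from pairs of consecutive prophylactic doses.

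**The concern.** A sensitivity analysis of data integrity should change because doubtful data are gone, not because the denominator was left behind. A manual record marks a stretch when the diary was not capturing events. Once the record is removed, nothing is known about bleeding or dosing in that stretch, yet the rebuilt dataset would count it as observed and bleed-free. It would also read a missing dose as a dose not taken. A shift in ABR, weekly dose or interval would then mix two things: the influence of unsupported records, and an artefact of how they were removed. The regulator and the study report need the first without the second.

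**Working it through.** The documents state no ABR, no number of manual records and no number of reverted edits, so there is no plan figure to reproduce. The formulas below are the SAP's. Bleed rates, shares and gap lengths are assumptions. I also assume that the rebuilt datasets re-apply SAP 5.3.1 and 5.3.2, which Section 9 does not state.

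**1. Episodic regimen, ABR.** Time is set essentially by visit and regimen-change dates, so removing a share m of bleeds multiplies ABR by (1 − m).

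| Assumed ABR | m = 5% | m = 10% | m = 20% | Same share of time also removed |
|---|---|---|---|---|
| 10 | 9.5 | 9.0 | 8.0 | 10 |
| 20 | 19.0 | 18.0 | 16.0 | 20 |
| 30 | 28.5 | 27.0 | 24.0 | 30 |

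The last column assumes that bleeds in the removed window occur at the subject's usual rate.

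**2. Prophylaxis, ABR.** Assume 6 bleeds in 2 years (730.5 days): 6/730.5 × 365.25 = 3.00. One block holding 1 bleed is removed.

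- 14-day gap: 5/730.5 × 365.25 = 2.50 as planned; 5/716.5 × 365.25 = 2.55 with the time removed.
- 28-day gap: 2.50 as planned; 5/702.5 × 365.25 = 2.60 with the time removed.
- 60-day gap: 5/670.5 × 365.25 = 2.72 either way, because the 28-day rule already applies.

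Most of the fall from 3.00 is the loss of the bleed itself. The part due to keeping the time is 14/730.5 = 1.9% or 28/730.5 = 3.8% per block.

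**3. Prophylaxis, dose and interval.** Assume 40 IU/kg, 208 doses in 730 days, and 12 isolated doses removed.

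- Weekly dose: 208 × 40/730 × 7 = 79.8; after removal 196 × 40/730 × 7 = 75.2 IU/kg (−5.8%).
- Interval: 730/208 = 3.51 days; after removal 730/196 = 3.72 days.
- Dropping the 12 spanning intervals removes 24 of the 208 spacings, or 24 × 730/208 = 84.2 days. This leaves 184 × 40/645.8 × 7 = 79.8 IU/kg and 645.8/184 = 3.51 days.

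**4. Routes in the same re-run that raise ABR.**

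- A bleed-free prophylaxis block that leaves a gap over 28 days removes time but no bleed. With 6 bleeds, 35, 60 and 90 days give 3.15, 3.27 and 3.42 against 3.00. A bleed-free final block of 14 or 60 days gives 3.06 or 3.27.
- SAP 7.1.1 merges same-location treatment ("or injections less than or equal to 72 hours apart, are considered the same bleed"). With bleed injections at 0, 48 and 96 hours, losing the middle one leaves a 96-hour gap, so 1 bleed becomes 2.
- Deletions coded Error and D/EPD require subject confirmation, so they are reversed and the entries return. Per 100 bleeds, 5 removed with 0, 3, 5 or 8 restored as countable bleeds gives ratios of 0.95, 0.98, 1.00 or 1.03.

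**5. How to remove time on the episodic regimen.** Assume 48 bleeds in 24 months (one per 0.5 month) and 4 bleeds removed from a 2-month outage.

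- Time kept: 44/2 = 22.0.
- Outage window removed: 44/(2 − 2/12) = 24.0, the true rate.
- Cut from retained record to retained record: 4 consecutive bleeds span 5 spacings, or 2.5 months, giving 44/(2 − 2.5/12) = 24.6. If the 4 records are isolated, 4 months go: 44/(2 − 4/12) = 26.4.

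Episodic injections are given mainly for bleeds, so the retained-to-retained cut deletes real bleed-free time and overcorrects.

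**The case against.** The strongest reply is that this is a supplementary comparison of descriptive, secondary endpoints. SAP 9.1 already calls for counts of manual records by record and subject, and a listing of data changes before and after. SAP 9.3 adds per-subject listings of both sets of results. A careful reader could trace a shift to its source. Only manual records without full source verification go, and nothing shows that they form long blocks. On prophylaxis, longer gaps are already handled. All of this stands and limits the size. It does not supply the missing time rule, and listings do not correct a summary table.

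A reader might infer three stronger things that the documents do not support:

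- **That ABR in the assessment is forced down overall.** Step 4 shows upward routes, and without counts the net direction cannot be known. The duplicate route is limited, since same-location entries within 72 hours are not counted as new bleeds.
- **That the assessment favours the product.** It does not replace the main ABR. A fall on removal would leave the main result as the higher figure and would expose its reliance on unsupported records.
- **That code NBTFU conceals bleeds** ("New bleed deleted, follow up inj to existing bleed added (per protocol definition"). These edits need no subject confirmation and are not reversed. They therefore sit in both datasets and create no difference between them. For same-location bleeds the SAP 7.1.1 algorithm gives the same count anyway: injections at 0 and 50 hours are 1 bleed with or without the edit. The SAP 9.1 listing of changes would show them. What remains is narrow: the code states no location condition, so a different-location bleed merged by mistake would not be recovered. No such case is documented.

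**Conclusion.** The point holds for the removal step, in defined places. Removed bleeds leave the numerator while their time stays in the denominator for the whole episodic regimen and for prophylaxis gaps of 28 days or less. Removed prophylactic doses distort the re-run dose and interval tables. It does not hold for prophylaxis gaps over 28 days or for records at the end of a last prophylactic regimen, where time leaves with the records.

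The episodic effect is proportional to the share of bleeds removed. On prophylaxis, the part due to kept time is small per block (at most 28/730.5 = 3.8% over two years) but adds up over blocks. The dose example gives −5.8%. All sizes rest on assumed inputs; the real size and the net direction of the full re-run cannot be derived from the documents. The point deserves correction because the analysis answers a regulator's finding, but it does not affect the primary endpoint or the main ABR.

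**What to change.** Amend SAP Section 9 as follows.

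1. **Prophylaxis.** Treat any interval between retained injections that spans a removed manual record as missing, whatever its length. Take it out of the efficacy period and out of the SAP 6.5.3 dose and interval calculation. This extends the SAP's own 28-day rule.
2. **Episodic regimen.** Remove the documented diary-outage window, not the time between retained records. Where no outage dates exist, report ABR with the time kept and with the retained-to-retained time removed, as bounds (22.0 and 24.6 in the consecutive-record example, around a true 24.0).
3. **Separate steps.** Report results after record removal alone, after reversion of subject-confirmation changes alone, and after both, so that opposing effects can be seen.
4. **Optional, minor.** Set NBTFU edits back and let the SAP 7.1.1 algorithm re-apply the 72-hour same-location rule, much as SVC/L60 is already applied by program. Only different-location bleeds could change the count.

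The cost is slightly less follow-up time in the sensitivity re-run and some extra programming on datasets that are being rebuilt anyway. No new data are needed, apart from retrieving outage dates where sites recorded them.

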16. STATISTICAL METHODS AND DETERMINATION OF SAMPLE SIZE

In general, the data for subjects who enroll from parent studies will be integrated with their data from 8HA01EXT. A parent study is defined as a study where subjects may be enrolled into 8HA01EXT after study completion or at a time specified in the protocol.

All statistical analyses will be descriptive in nature. No formal comparison is planned and no hypothesis will be formally tested. Continuous variables will be summarized and presented by number, mean, median, standard deviation, minimum and maximum, and where appropriate, with the 25th and 75th percentiles. Categorical variables will be summarized by the number and percentage in each category.

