2.2.2. Secondary Efficacy Endpoints

The secondary endpoints are as follows:

- The annualized number of bleeding episodes (spontaneous and traumatic) per subject
- The annualized number of spontaneous joint bleeding episodes per subject
- The total number of days of exposure per subject per year
- The consumption of rFVIII Fc as total dose per kg per subject per year
- Physician's global assessment of the subject's response to his treatment regimen using a 4-point scale
- Subject's assessment of response to the treatment of bleeding episodes using a 4-point scale

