Subject recorded diary data was queried via a defined process which originally required confirmation with the subject of **all** changes. Subsequently, it was identified that this did not occur in all cases nor was this actually necessary for all types of change. In 2014, it was agreed that only certain categories of changes required subject confirmation, and a process implemented to ensure adequate documentation to support those changes was available. After a subsequent MHRA audit in 2015, further consideration was given to the timing of changes relative to the actual data generation, reliable subject recall period, and still lack of appropriate documentation to support changes in all cases. Therefore, taking into consideration these findings and industry standards to limit changes of subject reported data, the query process was updated to **only allow changes defined as not requiring subject confirmation**. Although changes classified as SVC/L60 did not require subject confirmation (as agreed with MHRA in 2014), these changes will no longer be made directly into the data, but will be applied via a programmatic data convention (details described in Section 5.4).

The Total Query Report (TQR) documents all changes to the EPD data. The changes in this report were classified according to a pre-defined list (see table below).

Code	Description	Requires subject confirmation
LN	Minor lot # change (addition/deletion of spaces or hyphens) and Major lot # change (any other changes to lot #)	N
D/EPD	Duplicate entry in EPD by subject - deleted	Y
D/CRF	Entry in EPROLOG is also in CRF/INFORM as in-clinic dose	N
Dose	Vials added or removed	Y
SVC	Single vials combined - entered as separate injections in error	Y
SVC/L60	Single vials combined - entered as separate injections in error – injection time range for combined records is ≤ 60 mins	To be applied via programmatic data convention during analysis as described in Section 5.4
Error	Subject entered in error - entry deleted	Y
DTOI	Date and/or time of injection corrected	Y
Pre-Fc	Entries deleted as prior to first dose with Fc (not required per protocol)	N
Train	Entries deleted as training/prior to first dose with Fc (not required per protocol)	N
Test subject	Subject does not exist - entries deleted	N

Code	Description	Requires subject confirmation

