9.2 Existing Outputs to be Re-run

The summary tables will be regenerated based on updated ADAM datasets are shown in Table 5.

Table 5: Summary Tables Rerun With the Updated Datasets

Outputs	Summary Table titles	Program file name
Disposition	Disposition	T-DISPOSITION.SAS
Exposure	Summary of exposure	T-EX-SUM.SAS.SAS
	Summary of prophylactic dose (IU/kg)	T-EX-PROPHY-DOSE.SAS
	Summary of prophylactic dose and interval	T-EX-PROPHY-DOSE-INT.SAS
ABR	Summary of annualized bleeding rate	T-ABR-SUM.SAS
Subject response to treatment of bleed	Summary of subject's assessment of response to rFVIII Fc injections for the treatment of bleeding episodes	T-SUBJ-ASSESS-RESP-BLD.SAS

Injections and dose required for resolution of a bleeding episode	Summary of number of injections required for resolution of a bleeding episode	T-INJ-RES-BLD.SAS
Injections and dose required for resolution of a bleeding episode	Summary of dose (IU/kg) of rFVIIIc for resolution of bleeds	T-DOSE-RES-BLD.SAS

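### The diary-edit impact assessment specifies no re-run summary for spontaneous joint ABR or annualized consumption, two secondary endpoints that draw on the fields being reverted

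*SAP*

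**What the plan says.** SAP 2.2.2 names six secondary endpoints. Two of them are "The annualized number of spontaneous joint bleeding episodes per subject" and "The consumption of rFVIII Fc as total dose per kg per subject per year".

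SAP Section 9 sets out a sensitivity analysis, under a commitment to the regulator, of how the diary query process and manually created records affected the study results. Every edit coded as needing subject confirmation returns to its original value. The classification table gives that code to "Change in Bleed Type", to bleed location, to most changes of injection reason, and to "Vials added or removed". Manual records not fully verified against a paper diary are removed. The analysis datasets are then rebuilt and some analyses repeated.

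The scope of the repeat is stated in three places:
- the Section 9 list that begins "Endpoints covered under the impact assessment include", which has five entries;
- Table 5 in 9.2, which has eight summary outputs and a single ABR output, "Summary of annualized bleeding rate";
- the impact-assessment part of the list of tables and listings at the end of the SAP body.

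None of the three names consumption or an ABR split by bleed type or location. The same list of tables plans all of these as separate outputs of the main analysis.

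**The concern.** The purpose of the assessment is to show whether edits without adequate confirmation altered the results. Spontaneous joint ABR depends on the recorded type and location of each bleed. Consumption depends on the IU recorded for each injection. These are the fields being reverted, yet no re-run summary is specified for either endpoint. If the outputs that are re-run look stable, a reader of the study report may assume that the stability extends to all the diary-based secondary endpoints, when two of them were not summarized on the reverted data.

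**Working it through.** No sample-size, power or alpha figure bears on this point. Protocol Section 16 states "No formal comparison is planned and no hypothesis will be formally tested". The check is a comparison of endpoints with outputs, followed by two illustrations.

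**Coverage of the six secondary endpoints**

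| Secondary endpoint (SAP 2.2.2) | Re-run summary specified? |
|---|---|
| Overall ABR | Yes |
| Spontaneous joint ABR | No |
| Exposure days | Yes |
| Annualized consumption | No |
| Physician's global assessment | No, but recorded by the investigator at visits (7.3.4), so reversion does not act on it directly |
| Subject's assessment of response | Yes |

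Of the eight Table 5 titles (disposition; exposure; prophylactic dose; prophylactic dose and interval; ABR; subject response; injections per bleed; dose per bleed), none mentions consumption, joint, location or bleed type.

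**Can overall ABR stand in for spontaneous joint ABR?** SAP 7.3.1 counts spontaneous, traumatic and unknown-type bleeds together. SAP 7.1.1 gives ABR = bleeds / efficacy days × 365.25. Take an assumed subject with 6 treated bleeds in 730.5 efficacy days, 3 of them recorded as spontaneous joint after edits.
- Overall ABR: 6 / 730.5 × 365.25 = 3.0.
- Spontaneous joint ABR: 3 / 730.5 × 365.25 = 1.5.
- If undoing type edits leaves 1 spontaneous joint bleed: 1 / 730.5 × 365.25 = 0.5. If it leaves 5: 5 / 730.5 × 365.25 = 2.5.
- Overall ABR is 3.0 in every case.

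A location edit can move overall ABR only by changing whether two records count as one bleed under the same-location 72-hour rule in 7.1.1.

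**Can the re-run dose tables stand in for consumption?** SAP 6.5.4 defines consumption as all IU/kg received in the efficacy period / efficacy days × 365.25. The re-run tables hold different quantities:
- Average weekly prophylactic dose (6.5.3) uses only pairs of consecutive prophylactic doses with no bleed between them.
- Dose to resolve a bleed (7.4.1) uses only bleed-treatment injections, summarized per episode or as a per-subject average, not as a yearly total.
- Exposure (7.3.2) counts days and injections, not IU/kg.

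A prophylactic dose whose next event is a bleed enters consumption but neither dose table. Vial strengths run from 250 to 3000 IU (Protocol 12.1). Reversing one vial edit on such a dose changes the total dose as follows:
- at an assumed 70 kg, by 250 / 70 = 3.6 to 3000 / 70 = 42.9 IU/kg;
- at an assumed 20 kg, by 250 / 20 = 12.5 to 3000 / 20 = 150 IU/kg.

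Over 365.25 efficacy days that is also the change in annualized consumption. Over a longer period it shrinks in proportion. Neither re-run dose table would register the change.

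**The case against.** A reader might infer that the assessment gives no answer at all for these two endpoints. The documents do not support that, for four reasons.

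1. **Other planned outputs.** SAP 9.1 counts edits by class, by record and by subject, and lists values before and after each change. SAP 9.3 plans by-subject listings of bleeding and injection results, dose results and exposure from both datasets, and allows bleed-level and injection-level listings if needed. The columns are not stated and the table shells are not among the documents, so spontaneous joint ABR or consumption might appear there. This stands. However, counts and listings do not give an original-versus-reverted comparison by regimen. The title of the impact dose listing also drops the reference to consumption that the main listing's title carries.

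2. **Consumption by components.** A large systematic effect of vial edits would probably show in the re-run prophylactic-dose and dose-per-bleed tables. This stands in part: those tables give a partial view, but they do not sum to the endpoint.

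3. **Bleed type.** Under SAP 7.1.1, where the subject or caregiver agreed with the investigator's reclassification, the investigator's type is analyzed whatever the diary shows. This may blunt some type reversals. It does nothing for location, vials, injection reason or removed records.

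4. **Declared subset.** Section 9 says openly that only certain analyses are repeated, and the wording that introduces its list need not be exhaustive. Table titles are described as provisional, and the underlying regulatory commitment is not available here. Even so, Table 5 and the output list are explicit, and both leave these outputs out.

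It is also fair that all analyses are descriptive and that the primary endpoint, inhibitor development, is a central-laboratory result untouched by diary edits.

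**Conclusion.** The point holds as a gap in specified outputs. Two of the six secondary endpoints, spontaneous joint ABR and annualized consumption, draw on reverted fields and have no re-run summary table. Four reverted edit classes (type, location, injection reason, vials) and the removal of manual records bear on them. Overall ABR cannot reflect a type reversal, and the dose tables reflect vial edits only partly.

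Two stronger readings should be avoided: that the assessment cannot inform these endpoints at all, and that the edits biased them. Section 9.1 and 9.3 outputs may supply partial information, and the documents give no number of edits and no effect size. The figures above rest on an assumed subject and assumed weights of 20 and 70 kg; they show the mechanism, not an expected shift. The conclusion also assumes that Table 5 titles describe their content, which the separate main-analysis tables by type and by location support. The change should be made, but it does not touch the primary endpoint or any hypothesis test.

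**What to change.** Add three existing main-analysis tables to Table 5, to the Section 9 endpoint list and to the impact-assessment output list, run on the reverted datasets for the same subject groups as the main analysis:
- annualized rFVIIIFc consumption;
- ABR by bleed type;
- ABR by location and type, with a spontaneous joint row. The combinations spelled out in SAP 7.3.1 do not name that row, so confirm that it is there.

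State in 9.3 which endpoints the by-subject listings carry, including spontaneous joint ABR and consumption. The datasets are being rebuilt anyway and the programs are needed for the main report, so the cost is a few more tables and no new data.
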